**Appendix 1 QOR-40**

**Modified Quality of Recovery Survey: MQoR-40 Study Patient Number:** \_\_\_\_\_

**Date of Surgery:** \_\_\_ / \_\_\_ / \_\_\_

**How have you been feeling in the last 24 hours? (please circle one)**

	None of the time	Some of the time	Usually	Most of the time	All of the time
COMFORT					
Able to breathe easily	1	2	3	4	5
Have had a good sleep	1	2	3	4	5
Able to enjoy food	1	2	3	4	5
Feel rested	1	2	3	4	5
EMOTIONS					
Have a feeling of general well-being	1	2	3	4	5
Feel in control	1	2	3	4	5
Feel comfortable	1	2	3	4	5
PHYSICAL INDEPENDENCE					
Have normal speech	1	2	3	4	5
Able to wash, brush teeth, shave	1	2	3	4	5
Able to look after your own appearance	1	2	3	4	5
Able to write	1	2	3	4	5
Able to return to work/usual home activities	1	2	3	4	5
PATIENT SUPPORT					
Been able to communicate with MD	1	2	3	4	5
Able to communicate with family / friends	1	2	3	4	5
Able to communicate with visiting healthcare worker	1	2	3	4	5
Have support from family / friends	1	2	3	4	5
Have support from visiting healthcare worker	1	2	3	4	5
Able to understand instructions and advice	1	2	3	4	5

**Have you had any of the following in the last 24 hours? (please circle one)**

	None of the time	Some of the time	Usually	Most of the time	All of the time
COMFORT					
Nausea	5	4	3	2	1
Vomiting	5	4	3	2	1
Retching	5	4	3	2	1
Feeling restless	5	4	3	2	1
Shaking / twitching	5	4	3	2	1
Shivering	5	4	3	2	1
Feeling cold	5	4	3	2	1
Feeling dizzy	5	4	3	2	1
EMOTIONS					
Had bad dreams	5	4	3	2	1
Feeling anxious	5	4	3	2	1
Feeling angry	5	4	3	2	1
Feeling depressed	5	4	3	2	1
Feeling alone	5	4	3	2	1
Had difficulty falling asleep	5	4	3	2	1
PATIENT SUPPORT					
Feeling Confused	5	4	3	2	1

	None of the time	Some of the time	Usually	Most of the time	All of the time
PAIN					
Moderate pain	5	4	3	2	1
Severe pain	5	4	3	2	1
Headache	5	4	3	2	1
Muscle pains	5	4	3	2	1
Backache	5	4	3	2	1
Sore throat	5	4	3	2	1
Sore mouth	5	4	3	2	1

Please check that all questions have been answered.

Thank you for your assistance.

Date: \_\_\_ / \_\_\_ / \_\_\_

Time: \_\_\_\_\_ AM / PM

**Appendix 2 (STOP-Bang Questionnaire)**

**STOP-Bang Questionnaire**

	YES	NO
Snoring: Do you snore loudly (loud enough to be heard through closed doors)?		
Tired: Do you often feel tired, fatigued, or sleepy during daytime?		
Observed: Has anyone observed you stop breathing during your sleep?		
Blood pressure: Do you have or are you being treated for high blood pressure?		
BMI: more than 35 kg m  ?		
Age: over 50 year old?		
Neck circumference: >40 cm?		
Gender: Male?		
Total Score		
PACU Desaturation		

High risk of OSA: Yes to ≥3 questions.

Low risk of OSA: Yes to <3 questions.

Chung F, et al: BJA 2012; 108: 768-75

## Appendix 3 (LSD ARCI) 

### LSD\_ARCI Questionnaire

Question	True	False
My hands feel clumsy		
I have a weird feeling		
I have an unusual weakness of my muscles		
Some parts of my body are tingling		
I feel anxious and upset		
I have a disturbance in my stomach		
A thrill has gone through me one or more times since I started the test		
I notice my hand shakes when I try to write		
I feel an increasing awareness of my bodily sensations		
It seems I'm spending longer than I should on each of these questions		

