#### **Methods:**

- 1. Primary outcome:** QoR-40 at 24 hours
- 2. Size of study groups(s):**  
It would be required to have 36 patients per group in order to achieve 80% power to detect a 10 point difference on the QoR-40 instrument with an estimated standard deviation of 15. To compensate for drop-outs or loss to follow-up, 80 patients will be recruited and randomized.
- 3. Secondary outcomes:**  
Postoperative opioid consumption  
Postoperative pain scores  
Length of hospital stay (Hours)
- 4. Patient entry, exclusion and dropout criteria:**  
**Entry:** Age 18-64, surgery: laparoscopic gastric reduction (gastric sleeve or gastric bypass), ASA I, II, III; BMI >35kg/m^2, Fluent in English  
**Exclusion:** History of allergy to protocol medications, History of chronic opioid use, pregnant patients.
- 5. Drop out:** Conversion to an open surgical route, patient or surgeon request.
- 6. Protocol specific methods:** Patients will be recruited on the day of surgery. Informed consent will be signed. Participant will complete the preoperative QoR-40 questionnaire (appendix 1) along with the Stop-BANG questionnaire (appendix 2). All medication except for propofol will be dosed based on the adjusted body weight (ABW=Ideal body weight (IBW) + [0.4 X (actual body weight –IBW)] Patients will be randomized using a computer generated table of random number to 2 groups: Group K (ketamine) will receive 0.5mg /kg of ketamine bolus followed by an infusion of 0.5 mg/kg/hour of ketamine throughout the intraoperative period. Group P (placebo) will receive the same amount of saline. The investigators will be blinded to study drug. The medication will be prepared by the hospital pharmacy and is not involved with the case or data collection.  
Subjects will be premedicated with midazolam (0.02-0.04 mg/kg IV preoperatively. Routine ASA monitors will be applied. Anesthesia will be induced with remifentanyl infusion started at 0.1 mcg/kg/minute titrated to keep blood pressure within 20% of the baseline and propofol 1.5 -2.5 mg/kg. Tracheal intubation will be facilitated with succinylcholine (1-2 mg /kg). Anesthesia will

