be maintained with sevoflurane titrated to a bispectral index (BIS) between 40-60, remifentanyl infusion started at 0.1mcg/kg/min titrated to keep blood pressure within 20 % of baseline values, and neuromuscular blockade will be maintained with rocuronium that will be administered at the discretion of the anesthesiologist. Upon termination of the surgery, residual neuromuscular blockade will be antagonized with a combination of neostigmine 0.05mg/kg (to a maximum dose of 5mg) and glycopyrrolate 0.01 mg/kg . Remifentanyl will be discontinued at the time of the removal of the laparoscope from the abdomen and hydromorphone 10 mcg/kg IV will be administered. Ondansetron 4 mg IV and dexamethasone 4 mg IV will be administered to prevent postoperative nausea and vomiting. Study drug will be discontinued at the end of the surgical procedure as the dressings are being placed. Normothermia will be maintained intraoperatively using a forced air warming blanket (Bairhugger, Arizant healthcare INC, Eden Prairie, MN). Subjects will receive IV Hydromorphone in divided doses as needed to achieve a verbal rating score for pain <4 out of 10 starting in the operating room following extubation and in PACU. Metoclopramide (10 mg IV) will be used as rescue antiemetic. Patient-controlled analgesia, programmed to deliver 0.2 mg of hydromorphone every 10 minutes, will be instituted before the patient is discharged from the PACU. Before PACU discharge, the LSD ARCI questionnaire (appendix 3) will be completed by the patient to assess for other untoward effects of ketamine. Ketorolac 30 mg every 6 hours for 24 hours will be started when admitted to patient room. SpO2 will be monitored continuously for 24 hours after discharge from PACU. At 24 hours after surgery patients will complete the QoR-40 (appendix 1) instrument.

**Risks/Benefits:** Participants may not have any direct benefit from taking part in this study. Taking part in this study may help us determine whether the study drug increases 24 hour quality of recovery and decreases opioid requirements within 24 hours of the surgery.

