#### **Most Frequent:**

Delirium  
Hallucinations  
Mood changes  
Nightmares  
Tachyarrhythmia  
Tonic- Clonic Epilepsy  
Vocalization

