**Normal Saline (placebo):**

Hypernatremia

These side effects are uncommon with the lower dose range used in this study.

There is a risk of loss of confidentiality even though there are strict measures in place to prevent occurrence. Answering some of the questionnaires or surveys may make subject feel uncomfortable. The subject may skip to the next question if the question upsets them. There is a very slight risk of skin irritation from the pulse oximeter (Konica Minolta).

**Confidentiality:** Subjects' identity will be guarded by assigning a numerical code which is only known by the principal investigator and research coordinator. Data will be stored in department computer which is password protected. Each study subject will be assigned a study code number. The code will be used to link study data to patient identification (name) in a separate database. Subject data will be stored on secure computers at Northwestern University. Data access will be password protected and only available to study investigators. The data forms will be de identified after the chart review prior to analysis. 7 years post manuscript completion the data both electronic and paper will be destroyed using current departmental approved methods of destruction.

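### Four of the seven ketamine effects listed as most frequent have no item on any form shown, and no adverse-event outcome is prespecified

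*Combined protocol and SAP*

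**What the plan says.** The Side effects of ketamine section lists seven effects under Most Frequent: delirium, hallucinations, mood changes, nightmares, tachyarrhythmia, tonic-clonic epilepsy and vocalization. Under Less Frequent it lists bradycardia, hypotension, respiratory depression and vomiting. The text after the saline entry then says: "These side effects are uncommon with the lower dose range used in this study". I read this as referring to ketamine. No rate is given.

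Methods item 6 assigns one instrument to harm. Before PACU discharge the LSD ARCI "will be completed by the patient to assess for other untoward effects of ketamine". Appendix 3 (LSD ARCI) shows ten true/false items, among them "I have a disturbance in my stomach". The QoR-40 (Appendix 1) is completed before surgery and again at 24 hours.

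The primary outcome is the QoR-40 at 24 hours. Methods item 3 names three secondary outcomes: opioid consumption, pain scores and length of stay. None is an adverse-event outcome, and no section shown describes how adverse events are collected or reported. The Confidentiality section mentions data forms and a chart review without giving their contents.

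**The concern.** The issue is what the forms ask, not when they are given. The protocol names the effects it regards as most frequent, says it will assess untoward effects, and then uses a questionnaire that asks about almost none of them. Giving the ARCI at a different time would not help, because the items are absent.

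What is at stake is the safety side of the report. Followed as written, the trial yields a QoR-40 comparison and an ARCI score, with no required count by group of the named effects. It would have no specified data with which to check its own statement that these effects are uncommon at this dose. Some of the information may also be lost for good: a hallucination that nobody asks about may never reach a chart. The primary analysis is not affected.

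**Working it through.** **Step 1. Match each listed effect to every form shown.** The forms are the QoR-40 (Appendix 1, repeated at the end of the document), the STOP-Bang form (Appendix 2) and the LSD ARCI (Appendix 3).

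| Listed effect | LSD ARCI | Other form or measurement |
|---|---|---|
| Hallucinations | none (a weird feeling is not specific) | none |
| Tachyarrhythmia | none | none |
| Tonic-clonic epilepsy | none (the hand-shaking item is not specific) | none (shaking or twitching on the QoR-40 is not specific) |
| Vocalization | none | none (the QoR-40 speech item measures function) |
| Nightmares | none | QoR-40 item on bad dreams |
| Delirium | none | QoR-40 item on confusion, self-reported |
| Mood changes | anxious and upset | QoR-40 items on anxiety, anger and depression |
| Bradycardia | none | none |
| Hypotension | none | none |
| Respiratory depression | none | PACU Desaturation field on the Appendix 2 form; continuous SpO2 for 24 hours after PACU; QoR-40 item on easy breathing |
| Vomiting | none specific | QoR-40 item on vomiting |

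- Most Frequent: 1 of 7 has an ARCI item, 3 of 7 have an item on some form, and 4 of 7 (57%) have none.
- Less Frequent: 2 of 4 have partial capture and 2 of 4 have none.
- Both lists: 4 + 2 = 6 of 11 (55%) have no item.

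**Step 2. Group size.** The plan uses a 10-point difference, SD 15 and 80% power. Assuming two-sided alpha 0.05 (not stated), n = 2 × (1.96 + 0.842)² × 15² / 10² = 35.3, so 36 per group. The plan's figure reproduces. Allowing 10% loss, 72 / 0.90 = 80 randomized. That is 40 per group if allocation is 1:1, which is also not stated. None of this bears on the gap; it only sets the denominators.

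**Step 3. What counts could show.** With no events in n patients, the exact two-sided 95% upper limit is 1 − 0.025^(1/n).

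- n = 40: 1 − 0.025^(1/40) = 8.8%.
- n = 36: 1 − 0.025^(1/36) = 9.7%.

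The documents give no event rate, so the following rates are assumptions. At 5% in the ketamine group, 40 × 0.05 = 2 cases are expected and the chance of at least one is 1 − 0.95^40 = 87%. At 10%, 4 are expected and the chance is 1 − 0.90^40 = 98.5%.

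**Step 4. What counts could not show.** With 40 per group and no placebo events, the two-sided Fisher p-value is 2 × C(40,k) / C(80,k) for k ketamine events.

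- k = 5: 2 × 658,008 / 24,040,016 = 0.055.
- k = 6: 2 × 3,838,380 / 300,500,200 = 0.026.

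So at least 6 against 0 is needed to reach 0.05. Power at assumed rates (ketamine against placebo) is 1% for 5% v 0%, 21% for 10% v 0%, 11% for 10% v 2%, 36% for 15% v 2%, 41% for 20% v 5% and 64% for 20% v 2%. Counting would allow description, but rarely a demonstrated difference.

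**The case against.** The strongest reply is that the side-effect lists are a risk disclosure, not endpoints the plan promised to measure. The stated aims are quality of recovery and opioid requirement; there is no safety hypothesis. That is fair. A reader might infer that the trial intends to declare ketamine free of untoward effects, and nothing in the documents says so. What remains is that the plan does set out to assess untoward effects and chose a tool that misses most of those it lists.

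Three other strong readings also go too far.

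- **That the events would go unrecorded.** Routine monitors are applied, and data forms and a chart review exist, with contents not given. Some events may well be captured. What the documents support is that the plan does not require it.
- **That respiratory depression and vomiting are missed as well.** Both have partial capture, as the table shows.
- **That the gap is what stops the trial from showing whether ketamine caused these effects.** Step 4 shows that counts at this size would seldom settle causation either, particularly for effects the protocol calls uncommon.

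The QoR-40 also deserves credit. Its items are recorded one by one and nothing bars tabulating them by group, so the position is 3 of 7 covered by proxy rather than 1 of 7. No such tabulation is planned, however, and it would not reach the other four.

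**Conclusion.** The point holds as a gap in planned safety data. The only instrument assigned to ketamine's untoward effects does not cover most of the effects listed as most frequent: 4 of 7 have no item on any form shown, and the other 3 have only self-reported QoR-40 proxies, plus one ARCI item for mood. Bradycardia and hypotension also have no item. With no adverse-event outcome or recording procedure prespecified, counts by group are not required, and the trial could not support a statement about how often these effects occur at its dose.

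The conclusion rests on the forms and sections shown; the contents of the data forms and chart review are unknown. The 8.8% limit assumes 40 per group. It is worth correcting because the cost is small and some of the data may not be recoverable later.

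**What to change.** Add to Methods item 3 a descriptive safety outcome: the number of patients in each group with each effect listed under Most Frequent and Less Frequent, from start of study drug to the 24-hour assessment.

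- **Definitions.** Give each of the 11 effects a short definition, fixed by the sponsor in advance. Hypotension shows why this is needed: blood pressure is actively titrated during surgery, so an undefined yes/no entry could not be interpreted.
- **Recording.** Staff blinded to group record yes/no and time from the anesthesia and PACU records, the SpO2 data, and a direct question at the existing 24-hour QoR-40 contact.
- **Reporting.** Give counts and risk differences with exact 95% confidence intervals, without significance tests. State in the plan that the intervals will be wide and that the counts describe but do not establish causation.
- **LSD ARCI.** Describe it as a measure of subjective drug effect only.

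The cost is a one-page checklist and a few minutes per patient, using records and a contact that already exist. The downside is imprecise estimates. Treatment, sample size and the primary analysis do not change.

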**Appendix 3 QOR-40**

**Modified Quality of Recovery Survey: MQoR-40 Study Patient Number:** \_\_\_\_\_

**Date of Surgery:** \_\_\_ / \_\_\_ / \_\_\_

**How have you been feeling in the last 24 hours? (please circle one)**

	None of the time	Some of the time	Usually	Most of the time	All of the time
COMFORT					
Able to breathe easily	1	2	3	4	5
Have had a good sleep	1	2	3	4	5
Able to enjoy food	1	2	3	4	5
Feel rested	1	2	3	4	5
EMOTIONS					
Have a feeling of general well-being	1	2	3	4	5
Feel in control	1	2	3	4	5
Feel comfortable	1	2	3	4	5
PHYSICAL INDEPENDENCE					
Have normal speech	1	2	3	4	5
Able to wash, brush teeth, shave	1	2	3	4	5
Able to look after your own appearance	1	2	3	4	5
Able to write	1	2	3	4	5
Able to return to work/usual home activities	1	2	3	4	5
PATIENT SUPPORT					
Been able to communicate with MD	1	2	3	4	5
Able to communicate with family / friends	1	2	3	4	5
Able to communicate with visiting healthcare worker	1	2	3	4	5
Have support from family / friends	1	2	3	4	5
Have support from visiting healthcare worker	1	2	3	4	5
Able to understand instructions and advice	1	2	3	4	5

**Have you had any of the following in the last 24 hours? (please circle one)**

	None of the time	Some of the time	Usually	Most of the time	All of the time
COMFORT					
Nausea	5	4	3	2	1
Vomiting	5	4	3	2	1
Retching	5	4	3	2	1
Feeling restless	5	4	3	2	1
Shaking / twitching	5	4	3	2	1
Shivering	5	4	3	2	1
Feeling cold	5	4	3	2	1
Feeling dizzy	5	4	3	2	1
EMOTIONS					
Had bad dreams	5	4	3	2	1
Feeling anxious	5	4	3	2	1
Feeling angry	5	4	3	2	1
Feeling depressed	5	4	3	2	1
Feeling alone	5	4	3	2	1
Had difficulty falling asleep	5	4	3	2	1
PATIENT SUPPORT					
Feeling Confused	5	4	3	2	1

	None of the time	Some of the time	Usually	Most of the time	All of the time
PAIN					
Moderate pain	5	4	3	2	1
Severe pain	5	4	3	2	1
Headache	5	4	3	2	1
Muscle pains	5	4	3	2	1
Backache	5	4	3	2	1
Sore throat	5	4	3	2	1
Sore mouth	5	4	3	2	1

Please check that all questions have been answered.

Thank you for your assistance.

Date: \_\_\_ / \_\_\_ / \_\_\_

Time: \_\_\_\_\_ AM / PM
